8.1 Study design

Open, multicenter, non-pharmacological observational study.

[figure not shown]
Dipartimento Area Materno - Infatile

SC NEFROLOGIA E DIALISI PEDIATRICA – TRAPIANTI DI RENE – Direttore: [name]

[contact]

email: [contact]

Pediatric Idiopathic nephrotic syndrome

The PRECISE study is an open, multicenter, non-pharmacological biological study. The study will recruit a total of 310 INS patients and 40 controls. In details, the study will recruit 110 treatment-naïve childhood INS patients as a discover cohort, who will be followed for 12 months. At enrolment urine and blood samples will be collected as for normal clinical practice for the planned analysis. At the 12-month follow-up, patients will be classified according to international guidelines as steroid-dependent (SDNS)/frequent relapsing (FRNS) and infrequent relapsing nephrotic

Dipartimento Area Materno - Infatile

SC NEFROLOGIA E DIALISI PEDIATRICA – TRAPIANTI DI RENE – Direttore: [name]

[contact]

email: [contact]

syndrome (IRNS) (10). Additional assessments and biological samples will be performed according to the study flowchart and as described in the study procedure chapter. A homogeneous control group (n=40) by age of children undergoing sampling for minor urological surgical correction procedures will be also enrolled. In the validation phase, biological samples from an independent group of prevalent INS (200 cases) cases will be collected.

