9.1 STUDY POPULATION (incident patients)

Inclusion criteria

1. Clinical diagnosis of idiopathic nephrotic syndrome (nephrotic range proteinuria uPr/uCr ratio > 2mg/mg, hypoalbuminemia < 3.0 g/dl, oedema);
2. No previous treatment for INS
3. age between 1 and 18 years at onset
4. signed informed consensus

Exclusion criteria

1. Congenital or infantile nephrotic syndrome (age < 1 year old); secondary nephrotic syndrome; glomerulonephritis; autoimmune diseases; vasculitis.
2. Absence of signed informed consensus
3. previous treatments with prednisone or prednisolone for INS

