9.2 CONTROL GROUP

Inclusion criteria

1. Clinical diagnosis of minor congenital abnormalities of kidney and urinary tract
2. Absence of proteinuria (uPr/uCr < 0.2 mg/mg)
3. age below 18 years
4. signed informed consensus

Exclusion criteria

1. Immune-mediated diseases not associated with proteinuria (glomerulonephrities)
2. age > 18 Years

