SC NEFROLOGIA E DIALISI PEDIATRICA – TRAPIANTI DI RENE – Direttore: [name]

[contact]

email: [contact]

activation of specific signaling cascades by posttranslational modification (phosphorylation) we will also characterize the phospho-proteome. Phosphorylated peptides are enriched after standard isolation and purification with a special kit (High-Select Fe-NTA Phospho-peptide Enrichment Kit). For an unbiased serum proteomics approach, we can rely on the established fully automated clinical pipeline using liquid handling robots and state-of-the-art mass spectrometry platforms, including the latest generation Orbitrap Exploris 480. The approach enables the detection and quantification of on average 300 plasma/serum proteins per hour using a data-independent acquisition approach from a 5 µl sample volume.

12. Source Documents

Medical history and all clinical data collected during the study will be collected from each visit's medical records.

Local laboratory records will be used to collect laboratory analysis results.

13. Sample Size

As this is a descriptive and explorative study without inference in the primary endpoint, and given the incidence of childhood idiopathic nephrotic syndrome, which is considered a rare disease, the number of recruiting centers, we foresee enrolling in this study 110 treatment-naïve INS children. A homogeneous age control group of healthy children undergoing minor urological surgical corrections will be enrolled as a control group (n=40 children in 3 years). These numbers are the maximum we can recruit, but at the same time, we think that this study could serve as an important basis for appropriate studies in the future.

14. Data Management

A consortium was created under the direction of the Lead Unit (IRCCS Ca Granda of Milano, [name], Proposal Coordinator) with the Partners involved in the study. At the enrollment visit, a unique code will be assigned to each participant. The de-identification of the data will take place in such a way that people who access the database will not be able to trace the identity of the subjects in any way. Only local investigators will be able to trace the identity of the enrolled subjects.

The data necessary for the study will be recorded in a specific eCRF in a Data Management System validated according to national legislation, provided by the Scientific Management of the Foundation. The platform used will be RedCap (Research Electronic Data Capture).

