15.2 Secondary endpoints: analysis

Differences between two groups of patients for all the analysis conducted will be evaluated using Student's parametric T-test (in case of normality of variables distribution and homoscedasticity of variance) or Mann – Whitney's non-parametric test. The normality of the data will be evaluated by the Shapiro-Wilk test and the homoscedasticity assumption of the variance will be evaluated by the Hartley F-max test. In cases where more features are available than samples, regularized regression approaches, such as LASSO, or feature selection approaches will be used to identify potential combinations of features associated with a given outcome. Analyses of differences in continuous outcome measures between 3 or more levels of categorical features will take place through analysis of variance (ANOVA) using multiplicity-adjusted post-hoc tests by Dunnett or Tukey, as appropriate. Data analysis will be performed using GraphPad Prism software and P-values of 0.05 will be accepted.

16. Quality control

Only after the approval from ethics committee and regulatory authorities, centers will enroll patients who meet inclusion and exclusion criteria and will propose them to participate to the study signing the informed consent. The coordinating center will have access to all registered data to verify any anomalies and report them to the participating center. All data will be handled, registered, and reported in accordance with the good clinical practice. As Promoter, Fondazione IRCCS Ca' Granda Ospedale Maggiore Policlinico can carry out a quality check on the study at its discretion. In this case, the investigator should allow the monitor to directly access all relevant documentation and devote some of his or her staff time to the reviewer to discuss the results of the monitoring and any other aspects of the study. In addition, the regulatory authorities can carry out inspections. In

Dipartimento Area Materno - Infatile

SC NEFROLOGIA E DIALISI PEDIATRICA – TRAPIANTI DI RENE – Direttore: [name]

[contact]

email: [contact]

this case, the investigator must authorize the inspector direct access to all relevant documentation and devote part of his time and his staff to the inspector himself to discuss the results of the monitoring and any other aspects of the study.

17. Study limitation

This study is a pilot study and shows some risks associated with it. The following limitations can be highlighted:

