1. Due to the nature of the pathology (rare disease), one of the risks could be not reaching the number of recruited patients (annual incidence of 2-7/100,000 children). Our contingency plan will be the integration of additional ERKnet and ESCAPE Network centers through an addendum to the protocol.
2. The other limitation could be the absence of sample stability. Our contingency plan will be to define specific isolation workflow protocols, centralize the biobanking system, and perform sample stability tests for the different applications.
3. Another problem could be a difficult blood draw based on the age of the new-onset children recruited in the study. We will exclude Infantile N from the study to overcome this problem.

From the statistical side, all the data will be extensively scrutinized to ensure that misreporting is minimized. Potential confounders will be identified and assessed routinely throughout the analysis. Where possible, confounding factors will be adjusted for in the analysis. Where < 10% of missing data are present in a variable we will aim to impute missing data from other available data sources using a random Forest regression or classification approach. Variables with >20% missing values within a group will be kept aside and used only for descriptive quantitative evaluations. Statistical analysis using linear mixed effect models will ensure that data from the same individuals over time are properly considered.

18. Other aspects

The study will be conducted by the Standards of Good Clinical Practice, the ethical principles deriving from the Declaration of Helsinki.

The study and the related documentation will be presented to the competent Ethics Committee of each center. The study will begin only after receiving the authorizations requested according to the institution's internal procedures.

The Ethics Committee must also approve any changes to the protocol and advertising used to recruit subjects for the study, according to local regulations.

18.1 Informative note to subjects and consensus module to personal data treatment.

The investigators have the responsibility to obtain a signed informed consent by parents or legal

Dipartimento Area Materno - Infatile

SC NEFROLOGIA E DIALISI PEDIATRICA – TRAPIANTI DI RENE – Direttore: [name]

[contact]

email: [contact]

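### The control group has no lower age limit although patients must be at least 1 year old, and the simple group tests in Section 15.2 carry no age term, so patient-control differences in secondary endpoints may partly reflect age.

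*Protocol*

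**What the plan says.** **Eligibility.** Section 9.2 asks of controls only "age below 18 years". Its one age exclusion is at the upper end. Section 9.1 asks of incident patients "age between 1 and 18 years at onset" and also excludes "Congenital or infantile nephrotic syndrome (age < 1 year old"). Section 17, item 3, explains the exclusion of infants by difficult blood draws: "We will exclude Infantile N from the study to overcome this problem". That sentence concerns nephrotic infants. Section 9.2 contains nothing similar.

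**Intent.** Section 8.1 describes "A homogeneous control group (n=40) by age of children undergoing sampling for minor urological surgical correction procedures". Section 13 repeats it: "A homogeneous age control group of healthy children". Neither section gives an age band, a matching variable or a ratio.

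**Analysis.** Section 15.2 states: "Differences between two groups of patients for all the analysis conducted will be evaluated using Student's parametric T-test", with the Mann-Whitney test as the alternative. For three or more groups it names ANOVA with Dunnett or Tukey post-hoc tests. LASSO or feature selection is foreseen when features outnumber samples. Section 17 adds that confounders will be assessed and, as far as possible, adjusted for. It names neither age nor a method for the patient-control comparisons.

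**Where controls enter.** In Section 8.3, endpoints 3, 4, 6, 7 and 8 compare SRNS/SDNS, IRNS and healthy children.

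**The concern.** The eligibility rule does not deliver the property that the design claims for the control group. A centre that follows Section 9.2 to the letter may enrol infants as controls, while no infant can be a patient.

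If a marker changes with age in childhood, as can be expected of lymphocyte subsets, gene expression and serum proteins, a difference in age mix between patients and controls appears as a difference between disease and health. An unadjusted t-test, Mann-Whitney test or ANOVA cannot separate the two.

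What is at stake is the reading of the secondary results that use healthy children as the reference. For controls under 1 year a later adjustment would not fully help: no patient has that age, so a model could only extrapolate. That part has to be settled at recruitment.

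**Working it through.** The protocol gives no power or sample-size figure for these comparisons. Section 13 calls the study descriptive and presents its numbers as recruitment maxima, so there is no stated figure to reproduce.

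**Step 1. Age ranges side by side**

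| Group | Lower limit | Source |
|---|---|---|
| Incident patients | 1 year at onset | 9.1 |
| Controls | none | 9.2 |

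The ranges differ over the first year of life. No other control criterion closes the gap. Section 10.9 mentions a body weight above 12 kg, but ties it to the maximum blood volume and does not make it an eligibility rule.

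**Step 2. Which analysis applies**

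The five endpoints compare three groups, so ANOVA is the relevant test in Section 15.2, not a t-test of all patients against controls.

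**Step 3. Illustration of what an age-driven shift would do**

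Inputs from the protocol:
- 40 controls (8.1, 13).
- 110 incident patients (13: "we foresee enrolling in this study 110 treatment-naïve INS children").
- Significance level 0.05 (15.2).

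Assumptions:
- Patients split 55/55 between SRNS/SDNS and IRNS.
- No disease effect, and normal data with equal SD.
- Age moves the control mean by d SD.

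With both patient groups at mean 0 and controls at d, the noncentrality of the F statistic is

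λ = d² × (110 × 40) / 150 = 29.33 d²

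with 2 and 147 degrees of freedom and a 5% critical value of 3.058. This λ depends only on the patient total, so the 55/55 split does not affect the overall F-test.

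| Shift d (SD) | λ | ANOVA F-test significant |
|---|---|---|
| 0 | 0 | 5% |
| 0.10 | 0.29 | 7% |
| 0.20 | 1.17 | 15% |
| 0.40 | 4.69 | 47% |

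A single Tukey contrast of one patient group of 55 with the controls is significant in about 3%, 8% and 33% of simulated trials at the same three shifts.

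**Step 4. What could produce such shifts**

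If a share f of controls is under 1 year and their marker level differs by D SD from that of older children, then d = f × D, ignoring the small extra variance:
- f = 10%, D = 1: d = 0.10.
- f = 20%, D = 1: d = 0.20.
- f = 20%, D = 2: d = 0.40.

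If the marker instead drifts steadily with age, the shift is smaller. Assume patients and the other controls average 5 years, infants average 0.5 years, and the drift is 0.05-0.15 SD per year. Then 10-20% infants give a mean-age gap of 0.10 × 4.5 = 0.45 to 0.20 × 4.5 = 0.90 years. The shift is 0.45 × 0.05 = 0.02 to 0.90 × 0.15 = 0.14 SD, which lies below the 0.20 row of the table.

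None of f, D, the mean ages or the drift is in the documents.

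**Step 5. Effect of removing controls under 1 year**

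In simulations of the pooled two-group t-test in which being under 1 year was the only age effect, leaving those controls out returned the false-positive rate to about 4-6%. Imbalance within 1-18 years would remain, and the eligibility line alone does not address it.

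**The case against.** The strongest case on the other side has five parts.

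1. **The plan as a whole can adjust.** Section 17 promises confounder adjustment as far as possible, Section 15.2 allows regression when features outnumber samples (likely for expression and proteome data), and age and sex are collected for all participants (Section 10.3). This stands. A reader might infer that the study has no way to adjust for age, and the protocol does not support that. What remains is narrower. The simple tests have no age term, the regression option is tied to a different condition, and the promise in Section 17 is not linked to the tests in Section 15.2.

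2. **Covariates belong in the SAP, which is not shown.** This is fair for the choice of model. It does not cover eligibility, which the protocol fixes and which no SAP can repair once the controls are recruited.

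3. **The bias may be small.** This also stands. A reader might infer false-positive rates up to about 90%. That needs a shift of 0.60 SD, for example a 4-year gap in mean age at 0.15 SD per year, and a pooled t-test of 110 against 40. Nothing in the documents supports such a gap, or even that controls will be younger, and the endpoints call for a three-group analysis.

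4. **The 12 kg condition may keep infants out in practice.** Possibly, but it qualifies a blood volume and does not define who may be enrolled.

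5. **The study is exploratory and 40 controls is the stated maximum.** This limits the weight of the point and argues against strict matching. It does not explain why the control criterion departs from the stated age homogeneity.

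**Conclusion.** The point holds in a limited form. Section 9.2 does not put into effect the age homogeneity stated in Sections 8.1 and 13, and the simple tests in Section 15.2 do not carry the adjustment that Section 17 promises. Differences between patients and healthy children in endpoints 3, 4, 6, 7 and 8 may therefore be partly age differences.

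The size cannot be derived from the protocol. The rates in the working show only how sensitive a comparison with 40 controls is to a given shift. They rest on assumed shifts, normal data and no disease effect, and they are not a forecast.

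A reader might extend the point to the predictive model. The primary objective separates SRNS/SDNS from IRNS among patients and uses no controls, so it is untouched. This is an inexpensive improvement to secondary analyses and does not challenge the main design.

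**What to change.** - **Section 9.2:** give controls the same 1-18 year range as patients.
- **Sections 8.1 and 13:** say how age homogeneity will be reached, for example by recruiting the 40 controls across the age bands of the incident cohort as far as feasible. Strict matching is not needed.
- **Section 15.2 or the SAP:** make the patient-control comparisons for endpoints 3, 4, 6, 7 and 8 with linear models (ANCOVA) that include age and sex, and refer to the commitment in Section 17. Transform or use ranks where the data are not normal.

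The cost is one eligibility line, one sentence on recruitment and some analysis wording. No new data are needed. The downside is slightly slower control recruitment, which matters somewhat because Section 13 presents 40 as the most that can be recruited. The eligibility change should come before control recruitment is complete, since it cannot be made afterwards without dropping controls.

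### The controls are described as homogeneous by age, but Section 9.2 sets no lower age limit, so infants with no counterpart among the patients can enter the secondary patient–control comparisons

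*Protocol*

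**What the plan says.** Two sections state the intended make-up of the control group. Section 8.1: "A homogeneous control group (n=40) by age of children undergoing sampling for minor urological surgical correction procedures will be also enrolled". Section 13: "A homogeneous age control group of healthy children undergoing minor urological surgical corrections will be enrolled as a control group". Neither says how age homogeneity will be obtained; no matching, bands or strata are described.

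The criteria that sites apply are in Section 9.2. Inclusion criterion 3 is "age below 18 years", and exclusion criterion 2 removes only those older than 18. Nothing is said about a minimum age.

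Both patient groups have one. Section 9.1 requires "age between 1 and 18 years at onset" and excludes "Congenital or infantile nephrotic syndrome (age < 1 year old"; Section 9.3 repeats both limits for the validation cohort.

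Section 8.3 compares SRNS/SDNS, IRNS and healthy children in endpoints 3, 4, 6, 7 and 8, and describes the healthy group in endpoint 9. For group differences, Section 15.2 names the t-test or Mann–Whitney test for two groups and ANOVA with Dunnett or Tukey post-hoc tests for three or more.

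**The concern.** The design sections promise a property of the control group that the eligibility rule does not secure. Controls are the only one of the three populations without a lower age limit. They are children with minor congenital urinary-tract abnormalities undergoing minor surgery, and nothing in 9.2 stops a site from enrolling one in the first year of life.

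Such a child has no counterpart among the incident patients. If a marker differs between infants and older children, part of any patient–control difference is an age difference, and the healthy-children profile mixes in an age group that the patient cohorts exclude by design. Controls are sampled once (Section 10.1), and Section 13 calls the planned numbers the most that can be recruited, so a place filled by an infant is not easily recovered.

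**Working it through.** **1. Age limits side by side**

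| Population | Lower limit | Upper limit | Section |
|---|---|---|---|
| Incident patients | 1 year at onset | 18 years | 9.1 |
| Validation cohort | 1 year at onset | 18 years | 9.3 |
| Controls | none | below 18 (inclusion); above 18 excluded | 9.2 |

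**2. Which endpoints are exposed**

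The primary endpoint (8.2) contrasts patient groups with each other, so controls do not enter. Controls enter endpoints 3, 4, 6, 7, 8 and 9.

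Section 10.9, on additional blood for patients and controls, mentions a body weight above 12 kg in the parenthesis that caps the volume. If that is applied as a minimum, and if most children under 1 year weigh less (an assumption), most infants would drop out of the blood assays: endpoints 3, 4, 8 and the serum part of 7. The note is not repeated for urine, which is residual from routine tests. Endpoint 6 and the urine part of 7 therefore stay exposed on either reading.

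**3. Possible size (illustration)**

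The protocol has no power calculation to reproduce; 40 controls is a feasibility figure. Inputs from the protocol are 110 incident patients, 40 controls and a 0.05 level (two-sided assumed). Two inputs are assumptions: the infant share *f* among controls, and the infants' shift *d* in SD units. The true disease effect is set to zero.

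- Apparent difference = *f* × *d*. With *d* = 1.0 it is 0.10, 0.20 and 0.30 SD for *f* = 10%, 20% and 30%.
- Standard error of the pooled difference = √(1/40 + 1/110) = 0.185 SD.
- Rejection probability ≈ Φ(*fd*/0.185 − 1.96) + Φ(−*fd*/0.185 − 1.96). With *d* = 1.0 this gives about 8%, 19% and 37%.

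Simulation (40,000 runs per cell) adds the slightly wider spread that a mixed control group has. The Tukey columns follow the three-group layout of 8.3 and count any significant difference between a patient group and controls. The patient split is not given, so 55/55 is assumed; 70/40 and 80/30 give nearly the same rates (at *d* = 1.0: 5.4–5.8%, 12.4–12.7% and 24.9–25.5%).

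| Infants among controls | Pooled t-test, *d* = 0.5 / 1.0 / 1.5 | Tukey, *d* = 0.5 / 1.0 / 1.5 |
|---|---|---|
| 0% | 5.1% | about 3.6% |
| 10% (4 of 40) | 5.7 / 8.0 / 11.3% | 3.8 / 5.7 / 7.8% |
| 20% (8 of 40) | 8.2 / 17.7 / 33.2% | 5.6 / 12.4 / 24.1% |
| 30% (12 of 40) | 12.2 / 34.6 / 63.5% | 8.6 / 25.5 / 50.9% |

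The Tukey rate with no infants is below 5% because only two of the three pairwise comparisons are counted.

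**4. Cost of removing infants afterwards**

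Age is recorded for everyone (10.3), so infants could be dropped from a comparison. At 20%, 32 controls remain and the standard error becomes √(1/32 + 1/110) = 0.201, or 9% larger (0.201/0.185). At 30%, 28 remain: √(1/28 + 1/110) = 0.212, or 15% larger.

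**The case against.** The strongest reply has four parts.

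*Sections 8.1 and 13 state an aim and 9.2 an outer limit, so both can hold.* This is fair. A reader might infer two contradictory definitions of the control group, but the text does not go that far: controls could be chosen by age within 9.2. What stands is that no selection rule is given and the lower limit is open.

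*The weight note already keeps infants out.* It may, for blood. It is not an eligibility criterion, it does not reach residual urine, and it does nothing for age balance above infancy.

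*Confounding is handled.* Section 17 says confounders will be assessed and adjusted for where possible, and age is collected. A reader might infer from 15.2 that age will be ignored; the protocol does not support that, and naming covariates is commonly left to the analysis plan. Nor is the bias beyond repair, since infants can be left out. What stands is that adjustment cannot borrow patients of an age the cohort excludes, and that exclusion uses up control places.

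*The study is exploratory and the primary contrast is within patients.* This is correct and limits the weight of the point.

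Section 17 also leaves out infantile disease because blood draws are difficult. A reader might take that as a conflict with 9.2, but it concerns newly diagnosed patients, not surgical controls.

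**Conclusion.** The mismatch is real and modest. Section 9.2 as written does not deliver the age homogeneity stated in 8.1 and 13, and it admits control infants whose age group is barred from both patient cohorts. The consequence is limited to endpoints 3, 4 and 6–9 and is clearest for the urine vesicle endpoints (6 and the urine part of 7). It would be wrong to infer that the primary predictive model is compromised.

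The size cannot be derived from the protocol, which gives neither the expected control ages nor any marker's change with age. Under the planned three-group tests, few infants or a 0.5 SD shift do little harm (at most about 9% in the table). The inflation becomes material at about 20% infants with a shift of 1.0 SD or more. The unadjusted pooled t-test gives higher figures (about 8%, 18% and 35% at 1.0 SD), but it is not the three-group comparison that the endpoints describe.

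**What to change.** - In Section 9.2, change inclusion criterion 3 to the patients' range (age between 1 and 18 years) and word exclusion criterion 2 to agree with it at both ends.
- Reconcile 9.2 with the weight note in 10.9, so that it is clear whether the note limits who is sampled or only how much blood is drawn.
- To deliver the homogeneity stated in 8.1 and 13, fill the 40 control places in a few broad age bands that follow the ages of the enrolled patients, where feasible.

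The cost is two lines of eligibility text, one clarification and a short sentence on selection. Infants having urological surgery could no longer fill control places, so control recruitment may be slightly slower. The change is worth most before control enrolment is far advanced, because each control is sampled only once.
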